3.3.5 Removal of patients from therapy or assessments

3.3.5.1 Removal of individual patients from therapy

The trial medication has to be permanently discontinued in the following circumstances:

- The patient experiences signs of hepatic injury, defined in [Section 5.3.6.1](#).
- In the opinion of the Investigator, the patient experiences unacceptable adverse events despite dose adjustments and supportive care.
- Use of restricted concomitant treatment: as defined in [Section 4.2.2](#) “restrictions”.
- Pregnancy: If a patient becomes pregnant during the trial the investigational product needs to be stopped and the patient should be followed up until birth or otherwise termination of the pregnancy. The data of the patient will be collected and reported in the clinical trial report (CTR) until patient's last visit and any events thereafter will be reported in the BI drug safety database. Refer to [Section 5.3.6](#) for detailed information on event reporting in case of pregnancy.

Premature discontinuation: in case the patient discontinues study drug, it is of utmost importance for the robustness and integrity of the trial results that his/her lung function parameters and safety data are recorded until the end of the 52 weeks period. Thus all patients will be asked to follow their visit schedule until the end of the trial (refer to [Section 6.2.3](#)).

For patients who prematurely discontinue trial medication and are unable to complete the scheduled visits, every attempt will be made to get information on vital status at 52 weeks after randomization, as well as at the time of the data cut-off for the primary analysis and at the end of the trial.

In the following cases discontinuation of trial medication is highly recommended. Only in special circumstances, the Investigator, upon thorough assessment of all available clinical data and taking into consideration the potential risks associated with administration of nintedanib, may decide not to withdraw the trial medication, even though one or more of the below mentioned criteria are fulfilled. In such a case, continuation of treatment with trial medication should be discussed with the patient, and the decision and reasoning documented in the source data.

- Major surgery, including any abdominal or intestinal surgery.

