4.2.1.2 Management of liver enzyme elevation

Nintedanib can be associated with increased liver enzymes (see [Section 1.2](#)). Concomitant use of other drugs known to cause liver enzyme elevations should be evaluated. For a detailed guidance on how to manage liver enzyme elevations, please refer to [Table 4.2.1.2: 1](#).

Table 4.2.1.2: 1 Recommendations for managing liver enzyme elevations

	AST or ALT increase to			Signs of hepatic injury* (Section 5.3.6)
	>1.5x to <3x ULN	≥3x to <5x ULN and no signs of hepatic injury (see Section 5.3.6)	≥5x to <8x ULN and no signs of hepatic injury (see Section 5.3.6)	
Visit 2 (randomization)	Withdraw trial medication or justify continuation ¹	Withdraw trial medication	Withdraw trial medication	Withdraw trial medication
Any other Visit	Continue as planned ²	Reduce dose or interrupt trial medication ³	Interrupt trial medication	Withdraw trial medication
		Close observation ⁴ After 2 weeks or any time later	Close observation ⁴ After 2 weeks or any time later	CLINICAL EVALUATION OF HEPATIC-INJURY (Section 5.3.6)
	<3x ULN	≥3x ULN	< 3x ULN	≥3x ULN
	Reduced: return to initial dose. Interrupted: restart at reduced dose. Monitor bi- weekly for at least 8 weeks	Permanently discontinue trial medication Close observation ⁴	Restart at reduced dose Monitor weekly for 4 weeks, then bi-weekly for at least 8 weeks	Permanently discontinue trial medication. Close observation ⁴

Footnotes:

*Signs of hepatic injury are defined as

- ALT and/or AST ≥8 fold ULN
- ALT and/or AST ≥3 fold ULN and total bilirubin ≥2 fold ULN
- ALT and/or AST ≥3 fold ULN and unexplained INR >1.5
- ALT and/or AST ≥3 fold ULN and unexplained eosinophilia (>5%)
- ALT and/or AST ≥3 fold ULN and appearance of fatigue, nausea, vomiting, right upper abdominal quadrant pain or tenderness, fever and/or rash

¹ Investigator to confirm in writing that continuation is justified (e.g. intermittent fluctuation of transaminases).

² According to visit schedule. Consider additional control visits as adequate.

³ To be decided by Investigator, based on individual risk assessment.

⁴ Close observation: Re-test ALT and AST, alkaline phosphatase, total bilirubin, and eosinophils within 48 to 72 hours, then approximately 7 days, then approximately 2 weeks by using intermediate visit lab kit.

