4.2.2.2 Cautionary notes

Nintedanib is a substrate of P-gp and, to a minor extent, CYP3A4. Co-administration with oral doses of a potent P-gp and CYP3A4 inhibitors, e.g. ketoconazole, erythromycin, may increase exposure to nintedanib. In such cases, patients should be monitored closely. Management of adverse reactions may require interruption, dose reduction, or discontinuation of therapy with nintedanib.

Co-administration with oral doses of a potent P-gp and CYP3A4 inducers, e.g. rifampicin, carbamazepine, phenytoin, and St. John's wort may decrease exposure to nintedanib and should be avoided.

As the most common side effects known for nintedanib are GI effects i.e. diarrhoea, nausea and vomiting (see [Section 4.2.1.1](#)) the concomitant use of medication with an overlapping safety profile (e.g. mycophenolate mofetil) should be carefully considered.

Nintedanib is also associated with increases in liver enzymes and bilirubin. If in addition to the trial medication, a treatment is introduced that is known to induce AST/ALT elevations (e.g. methotrexate, bosentan), additional measurements of liver enzymes (ALT and AST, alkaline phosphatase, total bilirubin, and eosinophils) every 2 weeks for approximately 6 weeks, by using intermediate (a-visit) trial lab kit are recommended.

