5.3.3 Safety laboratory parameters

The laboratory tests at regular site visits will include:

Category	Laboratory test
Haematology	Red blood cell count (RBC) Haemoglobin (Hb) Haematocrit (Hct) Mean corpuscular volume White blood cell count including differential Platelet count
Biochemistry	Aspartate aminotransferase (AST) Alanine transaminase (ALT) Gamma-glutamyl transferase (GGT) Alkaline phosphatase (ALK) Creatine kinase (CK) Lactate dehydrogenase (LDH) Total protein Total bilirubin Brain natriuretic peptide (BNP at V2, V7, V9 and EOT) Creatinine Glucose (non fasting) Uric acid Thyroid stimulating hormone (only at V2, V7, V9, and EOT) β-HCG (at Visit 2 only)
Electrolytes	Sodium Potassium Calcium Chloride Inorganic phosphorus
Coagulation	International normalized ratio (INR) Activated partial thromboplastin time (aPTT) Prothrombin time (PT)
Urinalysis	pH, glucose, erythrocytes, leukocytes, protein, nitrite (semi-quantitative measurements; -, +, ++, +++)
Local Urine dipstick pregnancy test in all women of childbearing potential. If urine test is not acceptable to local authorities, a blood test must be done at a local laboratory.	

The laboratory tests at intermediate 'a' visits will include:

Category	Laboratory test
Biochemistry	Total protein, creatinine, electrolytes and liver function (AST, ALT, GGT, alkaline phosphatase, and total bilirubin)
Urinalysis	pH, glucose, erythrocytes, leukocytes, protein, nitrite (semi-quantitative measurements; -, +, ++, +++)
Local Urine dipstick pregnancy test in all women of childbearing potential. If urine test is not acceptable to local authorities, a blood test must be done at a local laboratory.	

At 'a-Visits', safety blood, pregnancy tests and urine samples will be collected and submitted to the central laboratory if needed for additional safety monitoring at the discretion of the Investigator (see [Section 4.2.2.2](#) for additional safety monitoring).

The samples and pregnancy tests may be collected at the office of a local doctor using trial specific lab kits that will be sent to a central laboratory for analyses. These kits will be provided to patients at study visits as applicable.

A maximum total amount of approximately 100 mL blood will be taken for standard safety laboratory during the course of Part A. In Part B, a maximum total amount of approximately 90 mL blood will be taken for standard laboratory depending of the time the patient will stay in Part B.

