The following events will be handled as “deemed serious for any other reason”. An AE which possibly leads to disability will be reported as an SAE.

AEs considered “Always Serious”

Every new occurrence of cancer of new histology must be reported as a serious event regardless of the duration between discontinuation of the drug and the occurrence of the cancer.

Cancers of new histology and exacerbations of existing cancer must be reported as a serious event regardless of the duration between discontinuation of the drug and the occurrence of the cancer.

In accordance with the European Medicines Agency initiative on Important Medical Events, Boehringer Ingelheim has set up a list of further AEs, which by their nature, can always be considered to be “serious” even though they may not have met the criteria of an SAE as given above.

The latest list of “Always Serious AEs” can be found in the RDC system. A copy of the latest list of “Always Serious AEs” will be provided upon request. These events should always be reported as SAEs as described above.

Adverse events of special interest (AESIs)

The term AESI relates to any specific AE that has been identified at the project level as being of particular concern for prospective safety monitoring and safety assessment within this trial, e.g. the potential for AEs based on knowledge from other compounds in the same class. AESI need to be reported to the Sponsor’s Pharmacovigilance Department within the same timeframe that applies to SAE, see [Section 5.3.7](#).

Adverse events relating to gastrointestinal perforation and hepatic injury will be considered AESIs.

Hepatic injury

In this trial protocol, signs of hepatic injury are defined as:

- ALT and/or AST ≥ 8 fold ULN
- ALT and/or AST ≥ 3 fold ULN and total bilirubin ≥ 2 fold ULN*
- ALT and/or AST ≥ 3 fold ULN and unexplained INR > 1.5 *
- ALT and/or AST ≥ 3 fold ULN and unexplained eosinophilia ($> 5\%$)*
- ALT and/or AST ≥ 3 fold ULN and appearance of fatigue, nausea, vomiting, right upper abdominal quadrant pain or tenderness, fever and/or rash

* in the same blood draw sample.

These lab findings constitute a hepatic injury alert and the patients showing these lab abnormalities need to immediately stop the trial medication and need to be followed up according to the “drug-induced liver injury (DILI) checklist” provided in the ISF. The investigator is asked to collect requested information within 48 hours upon laboratory hepatic injury alert/notification.

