Potential DILI cases are defined as AESIs, and are reported and processed following the SAE process on the respective SAE form.

In case of clinical symptoms of hepatic injury (icterus, unexplained encephalopathy, unexplained coagulopathy, right upper quadrant abdominal pain, etc.) without lab results (ALT, AST and total bilirubin) available, the Investigator should make sure these parameters are analysed, if necessary in an unscheduled blood test. Should the results meet the criteria of hepatic injury alert, the procedures described in the DILI checklist should be followed.

Intensity of AEs

The intensity of the AE should be judged based on the following:

Mild: Awareness of sign(s) or symptom(s) that is/are easily tolerated

Moderate: Enough discomfort to cause interference with usual activity

Severe: Incapacitating or causing inability to work or to perform usual activities

In addition the intensity of diarrhoea adverse events should be classified and recorded in the eCRF according to the Common Terminology Criteria for adverse events (CTCAE) version 4 ([R10-4848](#), Table 5.3.6.1:1).

Table 5.3.6.1:1 CTCAE Categorization for diarrhoea

CTCAE Grade	Diarrhoea
1	Increase of <4 stools per day over baseline
2	Increase of 4 to 6 stools per day over baseline
3	Increase of ≥ 7 stools per day over baseline; incontinence
4	Life threatening consequences
5	Death

Causal relationship of AEs

The definition of an adverse reaction implies at least a reasonable possibility of a causal relationship between a suspected medicinal product and an adverse event. An adverse reaction, in contrast to an adverse event, is characterized by the fact that a causal relationship between a medicinal product and an occurrence is suspected.

Medical judgment should be used to determine the relationship, considering all relevant factors, including pattern of reaction, temporal relationship, de-challenge or re-challenge,

confounding factors such as concomitant medication, concomitant diseases and relevant history.

Arguments that may suggest that there is a reasonable possibility of a causal relationship could be:

- The event is consistent with the known pharmacology of the drug
- The event is known to be caused by or attributed to the drug class.
- A plausible time to onset of the event relative to the time of drug exposure.
- Evidence that the event is reproducible when the drug is re-introduced.

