6.2.4 Dose reduction visit / dose increase visit

If a patient experiences a drug related adverse event, the dose can be reduced and the dose can be re-increased after recovery as described in [Section 4.2.1](#). In both cases, the patient will have to come back to a visit where the following will be performed:

- Physical examination including vital signs.
- Adverse events and concomitant therapy will be assessment since last visit.
- Local dipstick pregnancy test (if applicable).

- Safety blood and urine samples will be collected and submitted to the central laboratory.
- FlowScreen® spirometry (FVC) in the allowed time window will be performed.
- Trial medication will be collected and treatment compliance will be reviewed.
- IRT call for reduction or increase of the dose and trial medication dispensation.

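### INR is missing from every liver re-test list and from the intermediate-visit panel, so one mandatory withdrawal sign cannot be detected on those samples

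*Protocol*

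**What the plan says.** **The stopping rule.** Protocol 5.3.6.1 defines five signs of hepatic injury. One is ALT and/or AST at 3x ULN or more together with unexplained INR above 1.5, and the two must come from the same draw. On the consequence, 5.3.6.1 says: "These lab findings constitute a hepatic injury alert and the patients showing these lab abnormalities need to immediately stop the trial medication". Section 3.3.5.1 lists signs of hepatic injury under the heading sentence "The trial medication has to be permanently discontinued in the following circumstances".

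**The tests ordered.**
- Close observation (Table 4.2.1.2: 1, footnote 4), on the intermediate-visit kit: "Re-test ALT and AST, alkaline phosphatase, total bilirubin, and eosinophils within 48 to 72 hours, then approximately 7 days, then approximately 2 weeks".
- Monitoring after a hepatotoxic co-medication is added (4.2.2.2): "ALT and AST, alkaline phosphatase, total bilirubin, and eosinophils) every 2 weeks for approximately 6 weeks, by using intermediate (a-visit) trial lab kit".
- Biochemistry at intermediate visits (5.3.3): "Total protein, creatinine, electrolytes and liver function (AST, ALT, GGT, alkaline phosphatase, and total bilirubin". Urinalysis and pregnancy testing are the only other rows.
- Clinical symptoms of hepatic injury (5.3.6.1): "without lab results (ALT, AST and total bilirubin) available, the Investigator should make sure these parameters are analysed".
- Regular visits (5.3.3): a coagulation row with INR, aPTT and PT, and a haematology row with the white-cell differential.

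**The action at two weeks.** If ALT/AST started at 3x to below 5x ULN and has fallen below 3x, Table 4.2.1.2: 1 says: "Reduced: return to initial dose. Interrupted: restart at reduced dose". From 5x to below 8x, treatment is interrupted and then restarted at the reduced dose. If ALT/AST is still 3x or more, treatment stops permanently.

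**The concern.** A mandatory stopping rule should be measurable on the samples the protocol prescribes for liver follow-up. Here one of the five signs is not. The same-draw condition means that an INR from an earlier or later regular visit cannot supply it.

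The wording suggests an oversight. Footnote 4 and 4.2.2.2 add eosinophils, which serve the eosinophilia sign, but leave out INR, which serves the parallel sign. Section 5.3.6.1 counts unexplained coagulopathy among the symptoms that prompt testing, yet names no coagulation test.

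At stake is re-exposure of a patient whom the protocol's own rule would withdraw. Protocol 2.3 acknowledges that fatal drug-induced liver injury has occurred on nintedanib. The case would also leave no trace in the analysis: the SAP's hepatic-injury summary (5.4.4) and important-deviation check C5 (6.2) use the same definition, so an INR that was never drawn appears in neither.

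**Working it through.** The plan gives no figure to reproduce. The check compares the test lists with the sign, and then bounds the number of patients.

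**1. Where INR is listed**

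| Test list (Protocol) | INR | Eosinophils / differential |
|---|---|---|
| Close observation, 4.2.1.2 footnote 4 | no | yes |
| Co-medication checks, 4.2.2.2 | no | yes |
| Symptom-triggered test, 5.3.6.1 | no | no |
| Intermediate-visit panel, 5.3.3 | no | no |
| Regular-visit panel, 5.3.3 | yes | yes |

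INR is absent from 3 of 3 liver re-test lists and from the intermediate panel. The last column shows a second mismatch: eosinophils are ordered on the intermediate kit, but the panel for that kit has no haematology row. The eosinophilia sign is lost as well only if the kit follows 5.3.3; kit contents are not in the documents.

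**2. Which re-tests could change the action**
- 48 to 72 hours and about day 7: if ALT/AST is still 3x ULN or more, INR above 1.5 in that draw would force withdrawal. Without INR the table proceeds on the enzymes alone.
- Week 2: INR cannot change the action. At 3x or more the drug is stopped anyway; below 3x the sign cannot be met.

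So 2 of the 3 re-tests matter.

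**3. Conditions for a missed case.** INR exceeds 1.5 at an early re-test while ALT/AST is from 3x to below 8x ULN; bilirubin is below 2x ULN; no listed symptom is present; and ALT/AST is below 3x by week 2. The other conditions are needed because the 8x, bilirubin and symptom signs can be assessed at every re-test.

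**4. Ceiling on patients.** Inputs: 5.0% of nintedanib patients with ALT and/or AST at 3x ULN or more in the IPF trials (Protocol 1.2), and 300 patients per arm (7.7). Half and double that rate are assumptions to show a range.

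| Rate | Patients = rate x 300 | Early re-tests = patients x 2 |
|---|---|---|
| 2.5% (assumed) | 7.5 | 15 |
| 5.0% (IPF trials) | 15 | 30 |
| 10% (assumed) | 30 | 60 |

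Placebo (0.007 x 300 = 2.1) is left out because re-dosing placebo carries no drug risk. The true number is lower than the ceiling: the 15 include patients with a sign at detection, patients still at 3x or more at week 2, and patients already below 3x at the first re-test. No share meeting the INR sign is assumed, because the documents give none.

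**5. Other draws with no INR prescribed**
- Co-medication checks: 6 weeks / 2 weeks = 3.
- Laboratory time points to week 52: visits 3, 4, 5, 6, 6a, 7, 7a, 8, 8a and 9 = 10, of which 3 are intermediate visits.
- Part B (SAP Table 6.7: 4): weeks 60 (9a), 68 (10), 76 (10a) and 84 (11), so 2 of 4.

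The intermediate-visit counts are maxima, since those visits are done only as needed.

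**The case against.** The strongest reply is that INR is not prescribed, rather than undetectable. The reduce and interrupt columns of Table 4.2.1.2: 1 apply only without signs of hepatic injury, so an investigator must consider INR. Footnote 4 can be read as a minimum list, 5.3.3 allows extra sampling, and it also requires close monitoring when liver values rise. Dose-change visits take safety blood (6.2.4: "Safety blood and urine samples will be collected and submitted to the central laboratory"), probably the full panel. An elevation found at a regular visit has INR in the same draw. The missed case is narrow, and since nausea (24.5%) and vomiting (11.6%) were common on nintedanib in IPF, the symptom sign may often apply first. In the symptom-triggered test, right upper quadrant pain with raised enzymes is already a sign, and bilirubin covers icterus.

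Much of this stands as a limit on size; none of it closes the gap.
- The close-monitoring sentence points back to 4.2.1.2, whose list has no INR. Extra sampling is discretionary, and the initial site assessment in 4.2.1.2 names no tests.
- The dose-change visit helps mainly patients whose dose is reduced. For interrupted patients the restart visit comes after ALT/AST has fallen below 3x ULN, when no sign can be met, although an INR still abnormal would be seen.
- The liver-injury checklist in the investigator site file starts only after an alert, so it cannot supply the INR that triggers one.
- Regular visits are 12 to 16 weeks apart after Visit 6, far wider than the two-week re-test window.
- The symptom-triggered test still leaves INR unmeasured where it could decide, for example with encephalopathy.

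**Conclusion.** The concern holds. On intermediate-visit samples, co-medication checks and the 48 to 72 hour and day-7 re-tests, the tests the protocol orders cannot show the INR sign. Following the re-test rule as written can return to drug a patient whom 3.3.5.1 would withdraw.

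The size is small. The ceiling is 15 nintedanib patients and 30 early re-tests (7.5 to 30 patients and 15 to 60 re-tests at half to double the rate). It assumes that the IPF rate carries over to this population and that all 300 patients are treated; the true count is lower and cannot be derived. The conclusion rests on the lists as printed, since kit instructions outside the documents could add INR. The eosinophil mismatch is an internal inconsistency whatever the kit contains. Efficacy inference is not affected. This is a minor point, held with high confidence.

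**What to change.** Add INR to footnote 4 of Table 4.2.1.2: 1, to the monitoring list in 4.2.2.2, to the intermediate-visit panel in 5.3.3 and to the unscheduled test in 5.3.6.1. Add the white-cell differential to the 5.3.3 intermediate panel so that it matches footnote 4. Alternatively, state that liver re-tests use the regular-visit kit. No threshold, dose action or analysis needs to change.

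The cost is one or two extra tubes at draws already planned, for tests the central laboratory already runs at regular visits, plus an amendment of four short texts. The downsides are slightly more blood per re-test and handling instructions for local doctors' offices that collect samples.

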4.2.1.3 Management of acute ILD exacerbations

In case of acute ILD exacerbation (see [Section 5.2.4](#)), all treatment options considered adequate by the Investigator are allowed. The patient may interrupt study treatment for up to 8 weeks, if necessary (e.g. if short-term full anticoagulation is performed).

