4.2.2 Restrictions

4.2.2.1 Restrictions regarding concomitant treatment

The aim of the study is to investigate the efficacy and safety of nintedanib in patients whose progressive lung disease is the main contributor to morbidity.

Treatment of ILD

Immunomodulatory medications i.e. Azathioprine, cyclosporine, tacrolimus, Rituximab, Cyclophosphamide, mycophenolate mofetil, OCS have been utilized in the clinical practice for the treatment of ILD although their benefit-risk profiles in ILD have not been established and they are not approved for the treatment of ILD in most countries. In order to avoid the potential impact of these drugs on the assessment of the efficacy and safety of nintedanib in PF-ILD, their use will not be allowed at randomization and during the first six months of the treatment period.

Patients who receive any of these medications for the treatment of their ILD will have to discontinue these drugs prior to randomization. As the protocol requires that eligible patients progress despite treatment with these medications (i.e. do not or no longer benefit from these drugs), prohibition of these medications is considered justified. In case of acute worsening of PF-ILD during the treatment period, the use of any of these drugs after six months of study treatment will be allowed if judged necessary by the investigator.

Treatment of the underlying diseases associated with ILD

The largest group of patients with PF-ILD that has an underlying disease associated with ILD is the group of patients with CTD. Eligible patients with underlying CTD should have *stable* CTD defined as no initiation or withdrawal of therapy for CTD within six weeks prior to screening. In addition, investigators are encouraged to maintain the baseline treatment of CTD during the entire study unless change is medically indicated.

The majority of the eligible patients with CTD is expected to have RA and to be receiving disease-modifying anti-rheumatic drug (DMARD) e.g. methotrexate or TNF inhibitors. All approved RA/CTD medications are allowed at stable doses at Baseline (Visit 2) and during the study with the exceptions of the following, less frequently used medications:

Azathioprine, cyclosporine, tacrolimus, high dose steroids, and Rituximab. The use of these medications will not be allowed in this study. In addition, the following drugs used off-label for the treatment of RA/CTD will not be allowed throughout the study: Cyclophosphamide and MMF.

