The rationale for these limitations is that, as described above, these drugs have also been utilized in the clinical practice for the treatment of ILD. In order to avoid the potential impact of these drugs on the assessment of the efficacy and safety of nintedanib in PF-ILD, their use will not be allowed.

Patients whose RA/CTD is well managed by these medications should not be considered for participation in the current study. In case a change in the RA/CTD treatment to another non-restricted medication is indicated, the patient's disease has to be stable (i.e. no initiation of new therapy or withdrawal of therapy for CTD within 6 weeks prior to Visit 1) before entering in the current trial.

Table 4.2.2.1: 1 Medication restrictions

Restricted medications: Azathioprine, cyclosporine, tacrolimus, Rituximab, Cyclophosphamide, mycophenolate mofetil, OCS >20mg/day, investigational drugs		
	For ILD	For CTD
Baseline	Not allowed at V2*	Not allowed
Within first 6 months of study treatment	Not allowed	Not allowed
After 6 months of study treatment	Allowed in case of significant deterioration [#]	Allowed case of significant deterioration [#]
After EOT	Allowed	Allowed

* Wash-out periods to be observed as described in [Table 4.2.2.1: 2](#) below

[#] All can be used in case of clinically significant deterioration of PF-ILD or worsening CTD at the discretion of the Investigator, except for investigational drugs. Introduction of new therapy for CTD should be minimized.

Table 4.2.2.1: 2 Wash-out schedule. Wash-out rules apply only for medications used for ILD treatment.

Medication	Wash-out period
Azathioprine Cyclosporine Tacrolimus Mycophenolate mofetil OCS >20mg/day	4 weeks prior to Visit 2
Rituximab	6 months prior to Visit 2
Cyclophosphamide	8 weeks prior to Visit 2
Investigational drug(s)	4 weeks or 6 half-lives (whichever is longer) prior to Visit 1

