C5	Trial medication not permanently discontinued after signs of liver enzyme elevations were observed that a) are indicative of hepatic injury as defined in Section 5.3.6.1 of the CTP b) correspond to ALT or AST \geq 3 fold ULN despite dose reduction or treatment interruption for 2 weeks or more	All patients where signs of liver enzyme elevations are not dealt with according to the requirements of the CTP. Programmatic support will be required to flag patients who may fulfil the criteria, however a manual review of outputs is required Additional note: In the CTR Table it should show which criteria are violated; however, deviations of multiple sub-categories will only counted once towards the overall category..	None

Table 6.2: 1 Important protocol deviations (continued)

Category/Code	Description	Requirements	Excluded from
D	Concomitant Medication		
D1	Patients who received either azathioprine, cyclosporine, tacrolimus, Rituximab, Cyclophosphamide, mycophenolate mofetil, OCS >20mg/day for the treatment of ILD or CTD: a) within the first 6 months of study treatment b) after 6 months of study treatment without significant deterioration of ILD or CTD	
Patients should be flagged programmatically who take any of the aforementioned medications. It would have to be manually checked if:
 
a) Any of these medications is used during the first 6 months of study AND NO documentation of exacerbation of ILD is provided; or if the medication is used for the treatment of the CTD.
 
b) Any of these medications is used after 6 months of study medication AND NO documentation of worsening of the ILD or exacerbation of ILD is provided; or no documentation of worsening of the CTD is provided
 
Programmatic support will be required to flag patients who may fulfil the criteria, however a manual review of outputs is required
 
Additional note: In the CTR Table it should show which criteria are violated; however, deviations of multiple sub-categories will only counted once towards the overall category
	None

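### Protocol 4.2.1.3, 4.2.2.1 and 3.3.5.1 do not give one instruction for an acute ILD exacerbation in the first 6 months that is treated with a restricted drug

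*Protocol*

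**What the plan says.** **Protocol 4.2.1.3** (acute ILD exacerbations): "all treatment options considered adequate by the Investigator are allowed". It excludes no drug and sets no time limit. On trial drug it adds: "The patient may interrupt study treatment for up to 8 weeks, if necessary". An interruption with a maximum length implies that a restart is intended.

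**Protocol 4.2.2.1** (restricted drugs for ILD): "their use will not be allowed at randomization and during the first six months of the treatment period". The same section deals with acute events: "In case of acute worsening of PF-ILD during the treatment period, the use of any of these drugs after six months of study treatment" is allowed if the investigator judges it necessary. Table 4.2.2.1: 1 has a row headed "Within first 6 months of study treatment", marked as not allowed for both ILD and CTD. Its footnote on deterioration is attached only to the row for use after 6 months. The text below the tables permits added ILD therapy once Visit 7 is complete. The table restricts OCS only above 20 mg/day, while the text names OCS without a threshold.

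**Protocol 3.3.5.1**: the list of circumstances in which trial drug must be stopped for good includes "Use of restricted concomitant treatment: as defined in" Section 4.2.2. This is the mandatory list, separate from the later list where stopping is only strongly advised. The section closes with a general pointer to 4.2.1 for conditions that permit interruption.

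**SAP Table 6.2: 1, code D1(a)**: the requirements column asks reviewers to check whether "Any of these medications is used during the first 6 months of study AND NO documentation of exacerbation of ILD is provided". Early use for a documented ILD exacerbation is thus not an important deviation. The description column of the same row lists early use with no exception.

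**The concern.** Take a patient with an exacerbation in month 3 who is given a drug on the restricted list. Under 4.2.1.3 the treatment is permitted and trial drug may pause for up to 8 weeks. Under 4.2.2.1 the treatment is not permitted, and under 3.3.5.1 trial drug must then stop permanently. Two sites facing the same event could each follow the protocol and do opposite things.

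This is first a patient-management matter. It is also a data matter, because whether trial drug was permanently stopped enters several planned analyses:

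- exposure and time to premature discontinuation (SAP 5.4.3);
- the split between patterns 1 and 2 in the missing-data analyses (SAP 7.4.2.1.2);
- the on-treatment sensitivity analysis, which SAP 7.4.2.1.1 ranks first among the sensitivity analyses.

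**Working it through.** **Side-by-side reading, first 6 months, listed drug given for an acute exacerbation**

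| Source | Is the drug allowed? | What happens to trial drug? |
|---|---|---|
| Protocol 4.2.1.3 | Yes | May be interrupted, up to 8 weeks |
| Protocol 4.2.2.1 text | No; acute worsening is covered only after six months | Not stated |
| Table 4.2.2.1: 1 | No (OCS above 20 mg/day) | Not stated |
| Protocol 3.3.5.1 | Refers to 4.2.2 | Permanent discontinuation |
| SAP D1 description | Counted as a deviation | Not applicable |
| SAP D1(a) requirements | Not a deviation if an ILD exacerbation is documented | Not applicable |

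**Does 3.3.5.1 reach this case?** It cannot mean any use of a listed drug, since 4.2.2.1 allows such drugs after 6 months in addition to trial drug. It must mean use that 4.2.2 does not permit. Early use for ILD is not permitted there, so the clause applies unless 4.2.1.3 overrides 4.2.2. Neither 4.2.2.1 nor 4.2.1.3 says that it does.

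**Scale.** The documents give no exacerbation rate for PF-ILD. Two assumptions are needed: that the IPF rates in Protocol 1.2 apply, and that half of the 52-week events fall in the first 6 months. With 300 patients per arm, the count is 300 x rate / 2.

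| IPF trial | Nintedanib | Placebo |
|---|---|---|
| 1199.34 (phase III) | 300 x 3.6% / 2 = 5.4 | 300 x 9.6% / 2 = 14.4 |
| 1199.32 (phase III) | 300 x 6.1% / 2 = 9.2 | 300 x 5.4% / 2 = 8.1 |

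This gives about 5-9 on nintedanib and 8-14 on placebo. Replacing the half by a constant hazard, 300 x (1 - (1 - rate)^f) with f from 24/52 to 0.5, gives 5.0-9.3 and 7.6-14.8, which is nearly the same. Adding the phase II trial 1199.30 (2.3% and 13.8%) widens the range to about 3-9 and 8-21 (300 x 2.3% / 2 = 3.5; 300 x 13.8% / 2 = 20.7).

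These counts include every early exacerbation. Only patients who receive a listed drug meet the conflict, and the documents give no figure for that share. The counts are therefore upper limits under the stated assumptions.

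**What the handling changes.** A patient who permanently stops in month 3 but has a week 52 FVC is in pattern 2; one who restarts and stays on drug is in pattern 1. SAP sensitivity analyses 1 and 2 run only if pattern 2 has more than 10 patients, in both arms for analysis 1 and in the placebo arm for analysis 2, so a few patients can decide whether they run. In the on-treatment analysis the first patient contributes data only to about month 3, and the second contributes up to week 52.

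**The case against.** The best case against the point is that the sections cover different situations. Section 4.2.1.3 concerns an event defined in 5.2.4 by acute dyspnoea and new CT changes. The added-therapy rule in 4.2.2.1 concerns more gradual deterioration, with an FVC decline as its example. On the usual principle that a specific rule overrides a general one, 4.2.1.3 is the exception. SAP D1 follows that scheme: in the first 6 months only an exacerbation excuses ILD use, and later either worsening or exacerbation does. The pointer from 3.3.5.1 to 4.2.1 fits as well.

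This makes an exception plausible, and it may be what the sponsor intends. It does not settle the text. Section 4.2.2.1 speaks of acute worsening and still sets the six-month limit. The pointer in 3.3.5.1 is general and names neither exacerbations nor restricted drugs. The SAP does not instruct sites, and its D1 description omits the exception that its requirements contain.

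A reader might infer three stronger claims, which the documents do not support:

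- **That the primary result is at risk.** Protocol 7.3.1 and SAP 7.4.1 use all FVC data to week 52, including data after discontinuation, so the primary analysis is largely protected. Time to first exacerbation or death (SAP 5.2.2.1.3) is fixed by the first event, so later handling of trial drug cannot alter a recorded exacerbation.
- **That the inconsistency will differ by arm.** The phase III hazard ratios in Protocol 1.2 were 0.38 and 1.15, the latter with a 95% CI of 0.54 to 2.42. Protocol 7.7 says there are no published ILD data on which to base assumptions for the main secondary endpoints. A difference is possible but not established.
- **That 5 to 14 patients per arm will meet the conflict.** That treats the upper limits as estimates.

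**Conclusion.** The inconsistency is real and should be resolved. For a listed drug given for an acute exacerbation in the first 6 months, the protocol supports two incompatible instructions on the drug and on trial medication, and it states no exception.

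The size is modest. Under the phase III rates and the half-in-6-months assumption, at most about 5-9 nintedanib and 8-14 placebo patients of 300 per arm could be affected, and fewer if some exacerbations are treated without a listed drug. The consequences are for patient management, exposure and discontinuation summaries, patterns 1 and 2, and the on-treatment sensitivity analysis. The textual conflict does not depend on these counts.

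**What to change.** Reconcile Protocol 4.2.1.3, Protocol 4.2.2.1 with Table 4.2.2.1: 1, and Protocol 3.3.5.1, with explicit cross-references, so that they give one instruction on two questions: whether a listed drug may be used for an exacerbation in the first 6 months, and what happens to trial drug afterwards. In the same edit, make the text and table of 4.2.2.1 agree on OCS. Then make the description and requirements columns of SAP D1 match each other and the reconciled protocol. Which clinical rule applies is for the sponsor to decide.

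The cost is a protocol clarification and a short SAP edit. It needs no new data collection, sample-size change or change to the primary analysis.
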